## Study protocol

### Abstract

**Introduction:** Globally, nurse-led clinics(NLCs) have been developed to serve and follow up on patients who have just been discharged from the hospital. NLCs cognitive training program as a potentially effective and promising treatment for MCI patients.

**Methods:** The study is a single-blind, randomized-controlled trial. Eligible patients need to be diagnosed as MCI. Participants will be randomized into either a NLCs training group or a home-based training group. Both groups will undergo total 72hour across 12 months. The outcome measures will be assessed at baseline, at the 6 months and 12 months during the intervention. The primary outcome is global cognitive function, assessed by the 30-item the Mini-Mental State Examination (MMSE), and the secondary outcomes include changes in other neuropsychological assessments and in result of resting electroencephalography (EEG) .

**Results:** The trial is currently ongoing, and it is anticipated that recruitment will be completed in June 2025.

**Discussion:** This trial will evaluate the efficacy and safety of NLCs cognitive training in patients with MCI, and further explore the potential mechanisms by analyzing teh results of neuropsychological assessments and EEG.

Trial registration:

**Keywords:** mild cognitive impairment, nurse-led clinics, computerized cognitive training, randomized controlled clinical trial

## 1 Introduction

Cognitive impairment that is a syndrome with persistent cognitive impairment occurs on a continuum from mild, moderate, to severe states, which is manifested as one or more impairments in cognitive domains. There is a high prevalence of mild cognitive impairment (MCI) in China. Among adults aged 60 and above, there are about 38.77 million MCI patients with a prevalence rate as high as 15.5%. In addition, among nervous system diseases, 22.8% patients with Parkinson's disease and 34%~65% patients with multiple sclerosis also have cognitive impairment. The provision of social care and the hours of unpaid care by families for patients who are living with cognitive impairment currently costs amount to £15.7 (US \$21.6) billion and £13.9 (US \$19.2) billion a year respectively. Given the magnitude of the problem in terms of individuals or family affected and the costs associated with cognitive impairment, the prevention and treatment of cognitive impairment is currently a public health priority at the center of the global action plan (2017–2025), requiring new solutions to support patients and families in managing disabilities related to the disease.

In this context, the need to promptly intervene with cognitive training on residual capabilities is well known. Previous studies have shown computerized cognitive training (CCT) interventions could improve global cognitive function in patients with

MCI. At the same time, cognitive training can significantly improve the overall cognitive function of patients regardless of short-term ( $\leq 10$  weeks), medium-term (10~20 weeks) or long-term ( $\geq 20$  weeks) intervention. Furthermore, giving intensive training after the normal training dose maybe get preferable cognitive function improvement and effect maintenance.

The increasing prevalence of MCI and importance of CCT have led to a growing demand for cognitive training services in an outpatient setting. It is likely to be a critical point of continuous, sufficient dose and high quality cognitive training in the effect of CCT. Hence, remote guidance and detection by medical staff are important for patients to cognitive training to meet the individual needs. Globally, nurse-led clinics(NLCs) have been developed to serve and follow up on patients who have just been discharged from the hospital. NLCs are defined as clinical practice facilities where nurses have their own formalized and structured standard to address healthcare needs of patients and their families. The clinics are run by advanced practicing nurses (APNs) who can monitor and support MCI to persist in cognitive training for a long time after discharge. In each consultation, the APNs also equip their families with the knowledge and caregiving skills to deal independently with the numerous challenges faced by their loved ones, thereby reducing the feeling of caregiving burden. The novelty of nurse-led clinics in cognitive training, randomized controlled trials demonstrating the effectiveness of the solution is still scarce.

This trial is the first study to test the efficacy of nurse-led clinics cognitive training on MCI patients using a single-blind, randomized controlled trial design. We hypothesize that nurse-led clinics cognitive training can (a)decelerate or ameliorate cognitive decline, (b)ameliorate anxiety and depressive symptoms, (c)increase the quality of life for both patients and family members, (d)improve the ability of daily life, (e)reduce the incidence of agitation.

## 2 Methods

### 2.1 Study design

This single-center, single-blind trial. All participants will be recruited from Xuanwu Hospital, Capital Medical University, Beijing. This study will be reported in accordance with both the CONSolidated Standards of Reporting Trials (CONSORT) statement and the CONSORT statement for nonpharmacological interventions.

The participants will be randomized into either a NLCs training group or a home-based training group. Both groups will undergo 72, 1-hour sessions of NLCs training or 144, 30-minute sessions of home-based training across 12 months. The outcomes will be assessed at baseline, at 6-month and 12-month follow-up. The outcomes will include multiple neuropsychological assessments to examine the effect of NLCs training on cognitive functions, resting-state EEG to measure brain connectivity and neural activity.

### 2.2 Participants

Patients with MCI will be recruited according to the following inclusion and exclusion criteria.

### **2.2.1 Inclusion criteria**

1. Subjects with informed consent;
2. Literate Han Chinese, above the age of 18;
3. At least 6 years of education;
4. Neither normal nor demented according to the criteria of the Diagnostic and Statistical Manual of Mental Disorders, Fourth Edition, with a Clinical Dementia Rating(CDR)  $\geq 0.5$  on at least one domain and a global score  $\leq 0.5$ ; a Mini-Mental State Examination score  $\geq 20$  (primary school), or  $\geq 24$  (junior school or above).
5. having normal vision and hearing with/without corrective devices.

### **2.2.2 Exclusion criteria**

1. Severe aphasia, physical disabilities, or any other factor that might preclude completion of neuropsychological testing.
2. Clinically significant gastrointestinal, renal, hepatic, respiratory, infectious, endocrine, or cardiovascular system disease; cancer; alcoholism; drug addiction.
3. Illnesses affecting mobility or are unable to accept assessments or interventions that are required in this study.

### **Randomization**

Participants will be randomly allocated to either the intervention group or the control group in a ratio of 1:1. After participants have given their informed consent, randomization will be performed by an independent statistician who is blinded to the patient interventions using IBM SPSS Statistics Software following the sequence: Data/select cases/random sample of cases/exact 1 case of the 2 total cases. Afterwards, the sealed randomization codes and intervention number are sent out to each center.

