### **Blinding**

Radiologists, statisticians, and neuropsychologists who measure the outcomes will be blinded to the randomization status. Blinding will also be maintained for data management, outcome assessment, and data analysis. Participants and therapists cannot be blinded to the intervention they receive or provide.

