### 2.5.3 Primary outcome

The primary outcome measure is the score change in MMSE from baseline to the end of the intervention.

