## 2.6 Data collection

Inclusion and exclusion criteria will be assessed at screening. After written informed consent is acquired, the following data will be collected: demographic data (gender, age, education, and occupation); medical history; concomitant medications; and findings from a complete physical examination and neurological examination. Then, neuropsychological assessments, and EEG will be carried out. The follow-up assessments will be scheduled at 6-month and 12-month after intervention. The study schedule of the trial is shown in Table 1. The study flowchart is presented in Figure 1.

Table 1 Schedule of the trial

Time point	Study period			
	screening	baseline	6-month intervention	12-month intervention
Eligibility screen	×			
Informed consent	×			
Randomization		×		
Demographic data		×		
CDR	×			
Assessments				
MMSE	×	×	×	×
MoCA		×	×	×
WHO-UCLA AVLT		×	×	×
BNT		×	×	×
IADL		×	×	×
BI		×	×	×
HARS		×	×	×
GDS		×	×	×
CMAI		×	×	×
NPI		×	×	×
ZBI		×	×	×
EEG		×	×	×

[figure not shown]

FIGURE 1 The flowchart of this trial

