## 2.8 Sample size

There are no published randomized controlled trials on NLCs cognitive training or home-based cognitive training in MCI patients. In our preliminary experiments, the intervention resulted in improvement in MMSE scores (mean: 0.5 vs 0.04). According to these data, to obtain a statistical power of 90% with a significance level of 5%, the sample size needs to be 26 for each group. To allow for a maximum dropout rate of 20%, the sample size is set to 32 participants in each group.

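### Does a draw of one case from two make the allocation of 64 participants predictable?

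*Combined protocol and SAP*

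**What the plan says.** The Randomization section gives a 1:1 ratio and then the order of events. First: "After participants have given their informed consent, randomization will be performed by an independent statistician who is blinded to the patient interventions". The tool is SPSS and the menu path is "Data/select cases/random sample of cases/exact 1 case of the 2 total cases". After the draw, "the sealed randomization codes and intervention number are sent out to each center".

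Section 2.8 fixes the number to allocate: "the sample size is set to 32 participants in each group", so 64 in all. Section 2.1 describes a "This single-center, single-blind trial", so the plural reference to centers in the Randomization section is a clerical slip.

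The Blinding section keeps outcome assessors and statisticians unaware of allocation but accepts that "Participants and therapists cannot be blinded to the intervention they receive or provide". It does not say whether the people who enrol are among those therapists.

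The documents do not say what the two cases are, how often the draw is repeated, whether pairs follow order of entry, or when each sealed code is opened. Section 2.6 places the baseline tests after consent ("Then, neuropsychological assessments, and EEG will be carried out"), and Table 1 puts randomization and those tests in one column without an order.

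**The concern.** Read literally, choosing one of two rows allocates two people. The obvious way to reach 64 is to repeat the draw 32 times, and if each draw covers the next two entrants, every pair holds one participant per arm. That is a permuted block of fixed size two, the most predictable restricted scheme there is. At a single site with unblinded participants and therapists, past allocations could become known. Sealing a code does not hide an allocation that can be deduced.

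The stake is selection. A recruiter who can foresee the next arm may choose or time who is enrolled, and blinded assessment cannot undo a difference made before treatment starts. The Sample size section plans around a difference of only 0.5 − 0.04 = 0.46 MMSE points, so even a small shift could matter.

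**Working it through.** **Inputs.** 26 per group before dropout, 20% dropout, 32 per group and means of 0.5 and 0.04 (section 2.8); the 1-of-2 draw (Randomization). The documents give no block size, list length or SD.

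**The plan's own figure.** 26 × 1.2 = 31.2, rounded up to 32, which reproduces the stated number. Dividing instead, 26/0.8 = 32.5 gives 33, a difference of one per group. Either way the draw must serve about 64 people.

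**Predictability under each reading.** Take an observer who knows only the last allocation and guesses its opposite. Within a block of size 2m the guess is right with probability m/(2m − 1); across a block boundary, or for the first participant, it is right with probability 1/2.

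- *Pairs in order of entry:* 1 × 0.5 for the first participant, 32 × 1 for second members, 31 × 0.5 for the remaining first members. (0.5 + 32 + 15.5)/64 = 48/64 = 75%. Simulation gave 0.750.
- *One list, 32 of 64:* (0.5 + 63 × 32/63)/64 = 32.5/64 = 50.8%.
- *Separate draw per participant:* 50%.
- *Draw after both members of a pair have consented:* 50% at the time of enrolment, since neither allocation exists yet.

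An observer with a complete running tally guesses right at rate [m + 2^(2m−1)/C(2m, m) − 0.5]/(2m) and is certain for a share 1/(m + 1).

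| Reading | Last allocation only | Full tally | Certain allocations |
|---|---|---|---|
| Order-of-entry pairs, codes released singly | 75% | 75% | 32 of 64 |
| Half of one list of 64 | 50.8% | 57.1% | 64/33 ≈ 1.9 |
| Separate draws | 50% | 50% | 0 |
| Both members consent first | 50% | 50% | 0 |

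**Which reading do the documents support?** The stated order is consent, then draw, then dispatch of codes. That fits a draw made once both members have consented, and it also fits the other readings. The target of exactly 32 per group does not separate pairs from a single list, because both guarantee it. It counts somewhat against separate draws, which give an exact 32:32 split with probability C(64, 32)/2^64 = 1.83 × 10^18 / 1.84 × 10^19 ≈ 10%; but 32 is a planned size, not a promised split. No text singles out order-of-entry pairs.

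**Can the harm be sized?** Only by assumption. Suppose all 32 predictable slots were steered and each choice shifted expected MMSE change by an amount η. Steering in both directions shifts 16 of 32 in each arm, so the average bias is η/2 + η/2 = η; steering in one direction gives η/2 on average. The plan states no SD; back-solving from 26 per group gives 0.46 × √13/(1.960 + 1.282) = 0.51. With an assumed η of 0.25 in both directions, a z-test on 26 completers per arm would reject a true null 42% of the time at SD 0.51 and 7.4% at an assumed SD of 2.0.

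These rates are not bounds. For one-way steering, the number of predictable slots in the steered arm is Binomial(32, 0.5): the mean of 16 gives a bias of 0.125 and a rate of 14% at SD 0.51, but 21 slots (the 95th percentile) give 21/32 × 0.25 = 0.164 and about 21%. Nor do they describe the planned test, which section 2.9 sets as a repeated-measures ANOVA with a time-by-group term under intention to treat. The spread reflects the assumptions, not this trial.

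**The case for a change.** The strongest case for a change is that the omission is certain even if the harm is conditional. Repeating the only draw described is a natural reading. The 75% needs no knowledge of the pairing rule, only of the last allocation. One site with unblinded therapists makes that knowledge plausible. An independent statistician, consent before the draw and blinded assessors do not by themselves stop a recruiter from timing an enrolment. Clarifying would take a few sentences, and the allocation list could largely settle the matter: one successive pair in the same arm rules out order-of-entry pairs, while ten successive pairs all split 1:1 would arise under separate draws with probability 2^−10 = 0.1%.

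Much of this stands: the gap is real, the 75% is correct under its condition, and sealed codes are no answer to a deducible sequence. What does not stand is the step from gap to defect. Harm needs order-of-entry pairs, codes released one at a time, a recruiter who learns earlier allocations, a wish to steer, and selection that tracks the outcome. On the last point, "The primary outcome measure is the score change in MMSE from baseline to the end of the intervention", so choosing people by starting score matters only as far as that score predicts change. The documents support none of these links beyond making some of them possible. Re-blocking would help only if the unproven reading were true and allocations remained; the Abstract expected recruitment to finish in June 2025.

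**Conclusion.** No change to the plan follows. The Randomization section leaves out a detail of execution; it does not prescribe a faulty method. Under every reading, including a fixed block of two, arms are assigned at random in a 1:1 ratio, and without steering the comparison is unbiased. An independent statistician handed this text must decide how to reach 64, and several ordinary choices keep guessing at or near 50% from the last allocation.

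The size of the point is a predictability between 50% and 75%, with the upper end reached only if pairs follow order of entry and codes are released singly. No bias in MMSE change and no false-positive rate can be derived from the documents, because the shift from steering and the SD are both unstated. Section 2.1 commits the trial to CONSORT reporting, and the trial report is the natural place to describe how the sequence was made. The conclusion would be different if the allocation list showed order-of-entry pairs while allocations were still to be made; nothing in the documents shows that.

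The plural centers are a slip with no effect on the sequence. The third, traditional training in the Intervention section, which a two-way draw could not allocate, is a separate matter and says nothing about predictability.

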### **Blinding**

Radiologists, statisticians, and neuropsychologists who measure the outcomes will be blinded to the randomization status. Blinding will also be maintained for data management, outcome assessment, and data analysis. Participants and therapists cannot be blinded to the intervention they receive or provide.

### **Intervention**

CCT that is a multi-domain adaptive training program is used in this trial. Training paradigms include processing speed, attention, long-term memory, working memory, flexibility, calculation, and problem solving. To enable adaptive training, each task was designed with several difficulty levels. At the beginning, assignment tasks from these domains will be similar across participants. On each training day, five tasks (2 min per task, each three times, in total 30 min per day) will be assigned. Within each task, high accuracy ( $>80\%$ ) is required to upgrade. The training is thus also adaptive at participant level, with a similar setup but personalized progress across

participants.

Cognitive training in NLCs, CCT was given twice a week during 1-6 months and once a week during 7-12 month in nursing clinic. There is 60 minutes at a time. All the patients were capable of performing the training under the guidance of APNs. At the same time, according to the caregivers' feedback, APNs will give them the desired care guidance.

Cognitive training in home, CCT was given four times a week during 1-6 months and twice a week during 7-12 month in nursing clinic. There is 30 minutes at a time. Nurses teach patients to acquire and carry out CCT at home during hospitalization. Nurses set the daily reminder function at 9:00am through training system. The data results of each training will be automatically stored in the personal information database in the cloud. And, a training report will be generated, including training difficulty, training results and training time. Nurses can examine patients' training through the cloud.

Cognitive training in tradition, the Home Cognitive Training Manual for Alzheimer's Disease compiled by our research team was distributed. And, the patients and their families were given detailed health education on the definition, clinical manifestations, drug and non-drug treatment, home nursing, the significance of cognitive training and the methods of cognitive training. Meanwhile, we established connection with patients for later follow-up.

## 2.5 Outcome measures

### 2.5.1 Neuropsychological assessments

The intervention will be assessed by *the Mini-Mental State Examination (MMSE)* and *the Montreal Cognitive Assessment (MoCA)*, in which scores range from 0 to 30, with higher scores representing better general cognitive performance.

*The World Health Organization-University of California-Los Angeles Auditory Verbal Learning Test (WHO-UCLA AVL)* which scores range from 0 to 45 will be used to assess memory function, with a higher value representing a better outcome.

*The Boston Naming Test (BNT)* will be used to assess language performance, specifically visual naming ability.

*Instrumental activities of daily living(IADL)* and *barthel index* is defined as being whether able to complete activity ability.

*Hamilton Anxiety rating scale(HARS)*, *the geriatric depression scale(GDS)*, *the Cohen-Mansfield Agitation Inventory (CMAI)* and *neuropsychiatric Inventory(NPI)* will be used to measure neuropsychiatric symptoms.

*Zarit caregiver burden interview (ZBI)* will be used to assess the burden of caregivers.

### 2.5.2 Resting EEG

EEG was acquired using a 32-conductor Ag-AgCl electrode cap and amplifier (BioSemi, Amsterdam, Netherlands) with a 2048-Hz sampling rate. To reduce interference during signal acquisition, we ensured that the electrode resistance was<5 kΩ. During data collection, the participants were seated in a comfortable chair,

relaxed, refrained from speech or voluntary movements, and kept their eyes closed. The eyes-closed state was recorded for 5 min, and the data were stored on a computer for offline analysis.

### 2.5.3 Primary outcome

The primary outcome measure is the score change in MMSE from baseline to the end of the intervention.

### 2.5.4 Secondary outcome

The secondary outcomes for neuropsychological assessments include the score change from baseline to the 6-month and 12-month after intervention in other scales. The EEG results also dose.

## 2.6 Data collection

Inclusion and exclusion criteria will be assessed at screening. After written informed consent is acquired, the following data will be collected: demographic data (gender, age, education, and occupation); medical history; concomitant medications; and findings from a complete physical examination and neurological examination. Then, neuropsychological assessments, and EEG will be carried out. The follow-up assessments will be scheduled at 6-month and 12-month after intervention. The study schedule of the trial is shown in Table 1. The study flowchart is presented in Figure 1.

Table 1 Schedule of the trial

Time point	Study period			
	screening	baseline	6-month intervention	12-month intervention
Eligibility screen	×			
Informed consent	×			
Randomization		×		
Demographic data		×		
CDR	×			
Assessments				
MMSE	×	×	×	×
MoCA		×	×	×
WHO-UCLA AVLT		×	×	×
BNT		×	×	×
IADL		×	×	×
BI		×	×	×
HARS		×	×	×
GDS		×	×	×
CMAI		×	×	×
NPI		×	×	×
ZBI		×	×	×
EEG		×	×	×

[figure not shown]

FIGURE 1 The flowchart of this trial

## 2.7 Data monitoring

The study will comply with the Declaration of Helsinki. The neuropsychological functions of all participants will be evaluated by the same trained neuropsychologists. EEG data will be acquired according to the same parameters and using the same scanner.

## 2.8 Sample size

There are no published randomized controlled trials on NLCs cognitive training or home-based cognitive training in MCI patients. In our preliminary experiments, the intervention resulted in improvement in MMSE scores (mean: 0.5 vs 0.04). According to these data, to obtain a statistical power of 90% with a significance level of 5%, the sample size needs to be 26 for each group. To allow for a maximum dropout rate of 20%, the sample size is set to 32 participants in each group.

